1.2.6 Relapsed and/or Refractory Multiple Myeloma

The development of MLN9708 in patients with RRMM includes 2 Phase 1 dose-escalation single-agent studies (Studies C16003 and C16004).

Across these studies, 120 patients were treated, 60 in each study (Study C16003 with the twice-weekly schedule and Study C16004 with the weekly schedule). The MTD in Study C16003 was 2 mg/m² twice-weekly dosing based on DLTs of macular rash and thrombocytopenia (platelet count = $10 \times 10^9/L$). The MTD in Study C16004 was 2.97 mg/m² given weekly based on DLTs of diarrhea, nausea, vomiting, and erythema multiforme.

At the data cut-off, with 3 patients remaining on study, the median number of cycles administered in Study C16003 was 4 (range 1-61) with 33 (55%) patients treated for ≥ 4 cycles, 17 (28%) for ≥ 8 cycles, and 11 (18%) for ≥ 12 cycles. Across all patients treated, including above and below the MTD, dose reductions were needed once in 57% of patients, with ≥ 2 reductions needed in 20% of patients.

CONFIDENTIAL

STUDY DRUG: MLN9708

SCRI INNOVATIONS STUDY NUMBER: MM 42

FINAL PROTOCOL: 11 APRIL 2014

AMENDMENT NUMBER 3: 11 FEBRUARY 2016

VERSION 4

At the data cut-off, all patients in Study C16004 have discontinued treatment. The median number of cycles administered was 2 (range 1-24) with 19 (32%) patients treated for ≥ 4 cycles, 12 (20%) for ≥ 8 cycles, and 2 (3%) for ≥ 12 cycles. Across all patients treated including above and below the MTD, dose reductions were needed once in 33% of patients, with ≥ 2 reductions needed in 13% of patients.

Final study results suggest that single-agent MLN9708 has anti-tumor activity in heavily pretreated MM patients, with durable responses/disease control, and is generally well tolerated (Richardson et al. 2014, Kumar et al. 2014).

1.2.7 Newly Diagnosed Multiple Myeloma (NDMM)

Three Phase I/II studies are being conducted with MLN9708 in combination with standard anti-myeloma regimens; 2 in combination with LenDex (Studies C16005 [Berdeja et al. 2011, Richardson et al. 2012 (a), Richardson et al. 2012 (b), Kumar et al. 2013] and C16008 [Richardson et al. 2012 (a)]) and 1 in combination with MP (Study C16006 [San Miguel et al. 2012]). Study C16014 is a randomized, placebo-controlled Phase III study of MLN9708 or placebo in combination with LenDex. Please refer to the MLN9708 IB and SMA for further information.

1.2.8 Rationale for the Study

The use of autologous stem cell transplantation, proteasome inhibitors, and immunomodulatory drugs has transformed the treatment landscape of patients with multiple myeloma (Jemal et al. 2010, National Comprehensive Cancer Network. 2010, Kumar et al. 2008). Despite these advances, the vast majority of patients will eventually relapse and succumb to their disease. In patients with particular high-risk features, such as those with abnormalities of chromosome 17p, circulating plasma cells, extra medullary disease, and short remission duration following aggressive induction/stem cell transplantation the outcome is especially poor with progression-free survival of less than 2 years (Richardson et al. 2011, Drake et al. 2010, Kapoor et al. 2009, Neben et al. 2012, Jimenez-Zepeda et al. 2012). Allogeneic (using donor stem cells) stem cell transplantation is an appropriate treatment option in these high-risk patients.

Allogeneic stem cell transplant can achieve better control of multiple myeloma, but carries a higher mortality as a consequence of complications related to graft-versus-host disease (GVHD) (Kumar et al. 2011). In GVHD, donor cells recognize the recipient as a foreign object and mount an immune reaction. Haploidentical blood or marrow stem cell transplantation has historically been limited by unacceptable rates of GVHD, graft failure, and nonrelapse mortality. As a result, patients with this type of transplantation were previously excluded from this protocol. However, modern transplant techniques have remarkably reduced GVHD and have led to the increasing utilization of haploidentical donors. The feasibility of haploidentical transplantation has dramatically expanded the donor pool, making allogeneic transplantation available for the vast majority of patients (McCurdy and Fuchs 2015, Kanate et al 2015). With the introduction of Protocol Amendment 3, haploidentical allogeneic transplantation is allowed.

Proteasome inhibitors have an anti-myeloma effect and are often used as either initial treatment or at relapse in patients with multiple myeloma. Proteasome inhibitors have also been shown in pre-clinical and clinical models to stimulate allogeneic immune cells to eliminate myeloma cells

CONFIDENTIAL

STUDY DRUG: MLN9708

SCRI INNOVATIONS STUDY NUMBER: MM 42

FINAL PROTOCOL: 11 APRIL 2014

AMENDMENT NUMBER 3: 11 FEBRUARY 2016

VERSION 4

and at the same time reduce the incidence and severity of GVHD (Koreth et al. 2009, El Cheik et al. 2008, Kroger et al. 2006). The use of proteasome inhibitors after stem cell transplant can therefore prolong remissions after transplant and reduce the incidence of GVHD.

This study investigates the role of MLN 9708 as maintenance in patients that undergo allogeneic stem cell transplant for high-risk multiple myeloma and in patients with multiple myeloma that undergo allogeneic stem cell transplant due to relapsing after an autologous stem cell transplant.

2. STUDY OBJECTIVES

2.1 Primary Objectives

The primary objectives of this study are to assess the:

- Maximum-tolerated dose (MTD) of MLN9708 in this patient population
- Safety of MLN9708 when used as maintenance after allogeneic stem cell transplant for multiple myeloma.

2.2 Secondary Objectives

The secondary objectives of this study are to determine the:

- Progression-free survival (PFS) at 2 years after initiation of maintenance therapy
- Overall survival (OS) at 2 years after allogeneic stem cell transplant
- Incidence of graft-versus-host disease (GVHD) in patients receiving allogeneic stem cell transplant and maintenance with MLN9708
- Effect of MLN9708 on immune effector cells after allogeneic stem cell transplant.

3. STUDY PATIENT POPULATION AND DISCONTINUATION

3.1 Inclusion Criteria

Patients must meet the following criteria in order to be included in the research study:

1. Symptomatic multiple myeloma or asymptomatic myeloma with myeloma-related organ damage diagnosed according to standard criteria in patients who received allogeneic transplant due to high-risk prognostic features, such as, but not limited to:
 - Chromosome 17p, partial deletion (del(17p), t(4;14), t(14;16), t(14;20)
 - Plasma cell leukemia
 - Progression-free survival of less than 2 years after autologous stem cell transplant

CONFIDENTIAL

STUDY DRUG: MLN9708
FINAL PROTOCOL: 11 APRIL 2014
AMENDMENT NUMBER 3: 11 FEBRUARY 2016

SCRI INNOVATIONS STUDY NUMBER: MM 42

VERSION 4

2. Evidence of engraftment of neutrophils (absolute neutrophil count [ANC] >1000 cells/mm³) and platelets (platelets >60,000 cells/mm³ [dose escalation phase] and >50,000 cells/mm³ [dose expansion phase])
3. Achievement of at least a PR prior to allogeneic stem cell transplant.
4. Adequate liver function defined as:
 - Alanine aminotransferase (ALT) and aspartate aminotransferase (AST) ≤3.0 x the upper limit of normal (ULN)
 - Total bilirubin ≤2.0 x ULN
5. Adequate renal function defined as creatinine clearance ≥30 mL/min, estimated or calculated.
6. Aged ≥18 and ≤70 years, at time of enrollment
7. Ability to swallow oral medication
8. Absence of gastrointestinal symptoms that precludes oral intake and absorption of MLN9708 (nausea, vomiting, diarrhea, malabsorption)
9. Off antibiotics and amphotericin B formulations, voriconazole or other anti-fungal therapy for the treatment of proven, probable or possible infections (defined in accordance with the European Organization for Research and Treatment of Cancer/Invasive Fungal Infections Cooperative Group and the National Institute of Allergy and Infectious Diseases Mycoses Study Group [EORTC/MSG] criteria)
10. Eastern Cooperative Oncology Group (ECOG) Performance Status score of ≤ 2 (Appendix A)
11. Life expectancy ≥3 months
12. Male patients with female partners of childbearing potential and female patients of childbearing potential are required to use two forms of **acceptable** contraception, including one barrier method, during their participation in the study and for 90 days following last dose of study drug. Male patients must also refrain from donating sperm during their participation in the study (Appendix C).
13. Ability to understand the nature of this study, comply with the study procedures, and willingly give written informed consent before performance of any study related procedure not part of standard medical care, with the understanding that consent may be withdrawn by the patient at any time without prejudice to future medical care.

3.2 Exclusion Criteria

Patients who meet any of the following criteria will be excluded from study entry:

3. Patients who have progressive disease when compared to pre-transplant staging as defined by IMWG Uniform Response criteria for Multiple Myeloma (see Appendix E).
4. Umbilical cord blood transplant

5. Patients with > Grade 2 peripheral neuropathy with pain, or \geq Grade 3 peripheral neuropathy per National Cancer Institute Common Terminology Criteria for Adverse Events (NCI CTCAE) Version 4.0
6. Patients with uncontrolled bacterial, viral, or fungal infections
7. New York Heart Association (NYHA) Class III or IV heart failure uncontrolled angina, severe uncontrolled ventricular arrhythmias, or electrocardiographic evidence of acute ischemia or active conduction system abnormalities (see Appendix B). Prior to study entry, any electrocardiogram (ECG) abnormality at Screening has to be documented by the Investigator as not medically relevant.
8. Patients who are pregnant (positive beta-human chorionic gonadotropin [β -HCG]) or breastfeeding
9. Most recent chemotherapy \leq 21 days and \leq Grade 1 chemotherapy-related side effects, with the exception of alopecia
10. Use of a study drug \leq 21 days or 5 half-lives (whichever is shorter) prior to the first dose of MLN9708. For study drugs for which 5 half-lives is \leq 21 days, a minimum of 10 days between termination of the study drug and administration of MLN9708 is required.
11. Wide field radiotherapy (including therapeutic radioisotopes such as strontium 89) administered \leq 14 days or limited field radiation for palliation \leq 7 days prior to starting study drug or has not recovered from side effects of such therapy
12. Major surgical procedures \leq 14 days of beginning study drug, or minor surgical procedures \leq 7 days. No waiting is required following port-a-cath placement.
13. Ongoing or active systemic infection. Known diagnosis of human immunodeficiency virus, hepatitis B, or hepatitis C
14. Central nervous system involvement
15. Known allergy to any of the study medications, their analogues, or excipients in the various formulations of any agent.
16. Systemic treatment with strong inhibitors of cytochrome P450 (CYP) 1A2 (CYP1A2) (fluvoxamine, enoxacin, ciprofloxacin), moderate inhibitors of CYP1A2 (mexiletine, propafenone, and zileuton), strong inhibitors of CYP3A (clarithromycin, telithromycin, itraconazole, voriconazole, ketoconazole, posaconazole, and nefazodone), moderate CYP3A inhibitors (amprenavir, aprepitant, diltiazem, erythromycin, fosamprenavir, grapefruit-containing products including grapefruit juice, and verapamil), or clinically significant CYP3A inducers (rifampin, rifapentine, rifabutin, carbamazepine, oxcarbazepine, primidone, phenytoin, phenobarbital), or use of Ginkgo biloba or St. John's wort within 14 days before study drug administration in the study.
17. Presence of other active cancers or history of treatment for invasive cancer \leq 5 years. Patients with Stage I cancer who have received definitive local treatment and are considered unlikely to recur are eligible. All patients with previously treated in situ

CONFIDENTIAL

STUDY DRUG: MLN9708
 FINAL PROTOCOL: 11 APRIL 2014
 AMENDMENT NUMBER 3: 11 FEBRUARY 2016

SCRI INNOVATIONS STUDY NUMBER: MM 42

VERSION 4

carcinoma (i.e., non-invasive) are eligible, as are patients with history of non-melanoma skin cancer.

18. Psychological, familial, sociological, or geographical conditions that do not permit compliance with the protocol.
19. Graft versus host disease > Grade 2; or GVHD Grade 1 or Grade 2 which requires > 0.5 mg/kg methylprednisolone, or equivalent

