Exclusion Criteria:	
Patients who meet any of the following criteria will be excluded from study entry:
 
 1. Patients who have progressive disease when compared to pre-transplant staging as defined by IMWG Uniform Response criteria for Multiple Myeloma (see Appendix E). 2. Umbilical cord blood transplant 3. Patients with $>$ Grade 2 peripheral neuropathy with pain, or \geq Grade 3 peripheral neuropathy per National Cancer Institute Common Terminology Criteria for Adverse Events (NCI CTCAE) Version 4.0 4. Patients with uncontrolled bacterial, viral, or fungal infections 5. New York Heart Association (NYHA) Class III or IV heart failure uncontrolled angina, severe uncontrolled ventricular arrhythmias, or electrocardiographic evidence of acute ischemia or active conduction system abnormalities (see Appendix B). Prior to study entry, any electrocardiogram (ECG) abnormality at Screening has to be documented by the Investigator as not medically relevant. 6. Patients who are pregnant (positive beta-human chorionic gonadotropin [β-HCG]) or breastfeeding 7. Most recent chemotherapy ≤ 21 days and \leq Grade 1 chemotherapy-related side effects, with the exception of alopecia 8. Use of a study drug ≤ 21 days or 5 half-lives (whichever is shorter) prior to the first dose of MLN9708. For study drugs for which 5 half-lives is ≤ 21 days, a minimum of 10 days between termination of the study drug and administration of MLN9708 is required.

CONFIDENTIAL

STUDY DRUG: MLN9708

SCRI INNOVATIONS STUDY NUMBER: MM 42

FINAL PROTOCOL: 11 APRIL 2014

AMENDMENT NUMBER 3: 11 FEBRUARY 2016

VERSION 4

MM 42 PROTOCOL SYNOPSIS

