5. STUDY DESIGN

This is a Phase II, open-label, multicenter, non-randomized study to determine the feasibility of MLN9708 as maintenance after allogeneic stem cell transplant for multiple myeloma. Patients will be enrolled between Days 45 and 120 after allogeneic transplant and will receive MLN9708 on Days 1, 8, and 15 of each 28-day cycle for 6 cycles. Up to 18 patients will be enrolled in the dose-escalation phase to define the MTD of MLN9708. An additional 20 patients will be enrolled in the expansion phase at the MTD.

Up to 5 study sites are planned in the United States.

Dosing will start at 2.3 mg. If acceptable tolerability is demonstrated, escalations will be made to 3 mg and to the maximum-planned dose (MPD) of 4 mg. Once the MTD/MPD is determined, enrollment into the expansion phase will proceed at that dose. The study schema is presented in Figure 1.

[figure not shown]
CONFIDENTIAL

STUDY DRUG: MLN9708
FINAL PROTOCOL: 11 APRIL 2014
AMENDMENT NUMBER 3: 11 FEBRUARY 2016

SCRI INNOVATIONS STUDY NUMBER: MM 42

VERSION 4

Figure 1 Study Schema

MTD = Maximum-tolerated dose
MPD = Maximum-planned dose

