6.1 Dose Modifications Due to Hematologic Toxicity

Dose reductions or holds and initiation of supportive care are allowed as clinically indicated by the treating physician. Patients whose treatment is delayed due to toxicity will discontinue study drug or will proceed with the next cycle of treatment when toxicity has improved (as long as the toxicity resolves within 3 weeks) according to the dose modifications below. Treatment with MLN9708 will be held in any patient experiencing a DLT as described in Section 5.1.2 at any time during the study. Patients who experience a DLT in the first cycle of therapy will be discontinued from treatment with MLN9708. Dose modifications following treatment-related toxicity in subsequent cycles will be according to the dose modifications below.

Dose reductions for toxicity will be allowed. For patients in the first cohort, MLN9708 may be delayed, but not reduced. For patients in Cohorts 2 and 3, doses will first be delayed and then

CONFIDENTIAL

STUDY DRUG: MLN9708

SCRI INNOVATIONS STUDY NUMBER: MM 42

FINAL PROTOCOL: 11 APRIL 2014

AMENDMENT NUMBER 3: 11 FEBRUARY 2016

VERSION 4

reductions will be allowed based on clinical judgment of the treatment physician (see Figure 1). If persistent toxicity occurs despite dose delays and/or reductions, the patient will be removed from the study.

Any patients who require a treatment delay of more than 3 weeks due to treatment-related toxicity will be discontinued from study treatment, unless the treating physician and the Study Chair agree that continued treatment at lower doses is in the best interest of the patient.

6.1.1 Recommended MLN9708 Criteria for Beginning or Delaying a Subsequent Treatment Cycle & Dose Modifications for Treatment Associated Toxicity on Day 1 of a New Cycle

Treatment with MLN9708 will use a cycle length of 28 days. For a new cycle of treatment to begin, the patient must meet the following criteria:

- ANC must be $\geq 1,000/\text{mm}^3$.
- Platelet count must be $\geq 40,000/\text{mm}^3$.
- All other nonhematologic toxicity (except for alopecia) must have resolved to \leq Grade 1 or to the patient's baseline condition

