If the patient fails to meet the above-cited criteria for initiation of the next cycle of treatment, dosing should be delayed for 1 week. At the end of that time, the patient should be re-evaluated to determine whether the criteria have been met. If the patient continues to fail to meet the above-cited criteria, delay therapy and continue to reevaluate. The maximum delay before treatment should be discontinued will be 3 weeks or at the discretion of the Principal Investigator.

Table 4 Dose Modifications Due to Hematologic Toxicities within a Treatment Cycle (Day 8 and Day 15 of a Treatment Cycle)

Event	Action ^d
Neutropenia (ANC)	
ANC <0.5 x 10 ⁹ /L (Grade 4) or febrile neutropenia	Hold dose until recovery to ≤ Grade 2 [ANC ≥1.0 x 10 ⁹ /L], then resume MLN9708 at one lower dose level ^a (if applicable ^b). Note: If resolved in ≤5 days, then resume without a dose reduction.
Recurrence of ANC <0.5 x 10 ⁹ /L (Grade 4) or febrile neutropenia	Hold ^a dose until ANC recovery to ≤ Grade 2 [ANC ≥1.0 x 10 ⁹ /L], then resume MLN9708 at one lower dose level ^a (if applicable ^b).
Thrombocytopenia	
Platelets <30 x 10 ⁹ /L	Hold dose until improvement to platelets ≥30 x 10 ⁹ /L 
 • If resolved in ≤5 days, then resume without a dose reduction^c. • If resolved in >5 days but <3 weeks, then resume dose at one lower dose level^c (if applicable^b).

^a Hold MLN9708 treatment; do at least weekly CBC with differential until toxicity resolves (ANC recovery ≥1.0 x 10⁹/L and platelets ≥30 x 10⁹/L).

^b Patients on 2.3 mg of MLN9708 will not undergo a dose reduction.

^c Re-treatment criteria = ANC recovery ≥1.0 x 10⁹/L and platelets ≥30 x 10⁹/L.

^d Any patient who requires a treatment delay of more than 3 weeks due to treatment-related toxicity will be discontinued from study treatment, unless the treating Investigator and Study Chair agree that continued treatment at lower doses is in the best interest of the patient. ANC = absolute neutrophil count, CBC = complete blood count.

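### The chemotherapy exclusion has its grade sign reversed: it turns away recovered patients treated within 21 days and excludes nobody with unresolved Grade 2 or higher chemotherapy toxicity

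*Protocol*

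**What the plan says.** The lead-in to Protocol Section 3.2 states how the list works: "Patients who meet any of the following criteria will be excluded from study entry". Item 9 of that list reads "Most recent chemotherapy \leq 21 days and \leq Grade 1 chemotherapy-related side effects, with the exception of alopecia". Section 3.2 starts its numbering at 3, so the same criterion is number 7 in the synopsis, where the same less-than-or-equal sign stands before "Grade 1 chemotherapy-related side effects, with the exception of alopecia".

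Three other places bear on the intended meaning:

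- **Radiotherapy (Section 3.2 item 11).** This excludes a patient treated too recently, or one who "has not recovered from side effects of such therapy". The two parts are joined by 'or'.
- **Neuropathy and GVHD (items 5 and 19).** Both exclude the higher grades.
- **Starting a later cycle (Section 6.1.1).** The condition is "All other nonhematologic toxicity (except for alopecia) must have resolved to \leq Grade 1 or to the patient's baseline condition".

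On timing, Section 5 says "Patients will be enrolled between Days 45 and 120 after allogeneic transplant".

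**The concern.** A Grade 1 ceiling with an exception for alopecia is what one writes as a condition for treating a patient. Here it sits in a list of reasons not to treat, and it has not been negated. The item that should require recovery from chemotherapy therefore requires nothing of the kind.

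What is at stake is safety at entry. Other criteria limit many specific problems: neutrophils, platelets, liver and renal function, gastrointestinal symptoms that prevent intake, ECOG status, neuropathy, cardiac disease, infection and GVHD. None limits chemotherapy toxicity in general. A Grade 2 rash attributed to chemotherapy has no entry limit of its own, and Grade 2 fatigue is bounded only indirectly, by ECOG 2 or better. Both overlap with common effects of the study drug: Section 1.2.5 gives fatigue in 45% and rash in 40% of patients in the oral studies. Section 6.1.1 does not catch the problem later, because a return to the patient's baseline is enough to start a new cycle, and the unresolved grade is that baseline.

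There is a smaller compliance issue. A site that follows the evident intent may enrol a recovered, recently treated patient whom the text excludes, and Section 3.3 lists protocol violation as a reason to stop treatment.

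**Working it through.** The protocol gives no figure to reproduce here. The check is a truth table for item 9, then a timing calculation.

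**Truth table.** Inputs: chemotherapy 21 days ago or less ('recent') or more than 21 days ago ('older'), and the residual grade of chemotherapy toxicity. The cells show what item 9 alone does.

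| Rule | Recent, Grade 0–1 | Recent, Grade 2–4 | Older, Grade 0–1 | Older, Grade 2–4 |
|---|---|---|---|---|
| As written: ≤21 days and ≤Grade 1 | excluded | admitted | admitted | admitted |
| Sign corrected, 'and' kept: ≤21 days and >Grade 1 | admitted | excluded | admitted | admitted |
| Sign corrected, 'or': ≤21 days or >Grade 1 | excluded | excluded | admitted | excluded |

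As written, neither Grade 2–4 column is excluded, and the only excluded cell is the recovered, recently treated patient. Correcting the sign alone reverses the two 'recent' columns and leaves both 'older' columns as they were.

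**Could 'and' join two separate exclusions?** Then recent chemotherapy would exclude by itself, and so would toxicity of Grade 1 or less. That would bar every patient with little or no toxicity, and would still admit Grade 2 or higher toxicity once chemotherapy was more than 21 days past. This reading does not rescue the item.

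**Direction.** Items 5, 11 and 19 all screen out the worse state. Section 6.1.1 uses the same Grade 1 limit, also with alopecia excepted, as a condition for giving drug. An alopecia exception makes sense only in a rule that screens out unresolved toxicity.

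**Timing.** Item 9 does not say what the 21 days are counted back from. I count from entry; a later first dose would only lengthen the gaps. If conditioning ended by the day of transplant (Day 0, an assumption), the time since conditioning equals the day of entry:

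- earliest entry: 45 − 21 = 24 days outside the window
- latest entry: 120 − 21 = 99 days outside the window

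Without that assumption, chemotherapy given up to Day 23 after transplant is still outside the window for every patient, since the earliest entrant is 45 − 23 = 22 days from it. With 'and', item 9 therefore does not reach conditioning toxicity, whichever way the sign points.

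**What 'or' would add.** An unrestricted 'or' rule excludes Grade 2 or higher chemotherapy toxicity at any time since chemotherapy. That meets other parts of the protocol:

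- Inclusion 2 accepts "absolute neutrophil count [ANC] >1000 cells/mm³". As 1,000 cells/mm³ equals 1.0 × 10⁹/L, this is the level Table 4 treats as Grade 2 or better: "Hold dose until recovery to ≤ Grade 2 [ANC ≥1.0 x 10 ⁹ /L".
- Sections 3.1 and 3.2 set no haemoglobin or lymphocyte limit, and Section 5.3.1 permits erythropoietin and red-cell transfusion. Grade 2 anaemia or lymphopenia attributed to conditioning would become a new exclusion.
- Item 5 deliberately admits Grade 2 neuropathy.

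**The case against.** The strongest reply is that this is an obvious slip which most sites would read as intended, and that the correction proved by the documents does little. The sign matters only for chemotherapy in the 21 days before entry. Neither document describes planned chemotherapy in that interval, and patients who have progressed since pre-transplant staging are excluded. The residual gap is also narrow. The protocol knowingly accepts comparable states, such as Grade 2 neuropathy, ECOG 2, and GVHD up to Grade 2 on limited steroid, and it requires a baseline examination and GVHD assessment.

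Most of this stands. The group affected by the sign alone is probably small, and no computed figure in the protocol or SAP changes. It does not follow that the text can be left. This is an operative eligibility rule that says the opposite of its purpose in both places where it appears, and sites should not have to correct it silently.

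A reader might infer that correcting the sign would keep out patients with unresolved conditioning toxicity. It would not: the 'older' columns of the table do not change. A reader might also infer that 'and' is itself a proven error. The documents do not show that. A rule excluding recent chemotherapy with toxicity above Grade 1 is coherent. The radiotherapy item makes 'or' plausible but does not settle it.

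**Conclusion.** The item is wrong as written in Section 3.2 and in the synopsis. The reversed sign follows from the text alone, so confidence in it is high. Its direct effect is confined to patients with chemotherapy in the preceding 21 days: the recovered are turned away and the unrecovered are not excluded by this item. How many patients that is cannot be derived from the documents.

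The connector is an open question for the sponsor, not a finding of error. It carries the larger practical consequence, because with 'and' the item does not reach conditioning toxicity. The 24-to-99-day figure rests on conditioning having ended by the day of transplant.

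It would go too far to say that unsuitable patients were enrolled, or that DLT attribution was distorted. Nothing in the documents supports either statement.

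**What to change.** 1. **Certain.** In Section 3.2 item 9 and synopsis exclusion 7, change 'Grade 1 or less' to 'greater than Grade 1'. This is one symbol in two places and can go into the next amendment.

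2. **Query to the sponsor.** Ask whether 'and' should be 'or', to match the radiotherapy item and bring conditioning toxicity within reach. Ask at the same time what the 21 days are counted back from.

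3. **Only if 'or' is chosen.** Limit the toxicity half to non-haematologic side effects above Grade 1, except alopecia and toxicities with their own entry limit in Sections 3.1 and 3.2, such as neuropathy and liver tests. Possible wording: *most recent chemotherapy 21 days ago or less, or non-haematologic chemotherapy-related side effects above Grade 1, other than alopecia and toxicities limited elsewhere in Sections 3.1 and 3.2.* This keeps Grade 2 anaemia, lymphopenia or neutropenia from becoming a new exclusion in a trial of up to 38 patients.

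Step 1 costs almost nothing. Steps 2 and 3 need a clinical decision on the connector and on the list of exempt toxicities, but no new data collection and no change to the analysis.
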